6. STUDY SUBJECTS

6.1 INCLUSION CRITERIA

1. ≥ 18 years of age
2. Structural heart disease (post-MI, dilated cardiomyopathy, sarcoid myopathy, hypertrophic cardiomyopathy, etc.)
3. Planned for ICD implantation for:
 - i. Secondary prevention (e.g.: VT/VF arrest, sustained VT, syncope/inducible VT)
 - ii. Primary prevention + inducible MMVT during induction via ICD lead testing
 - iii. Primary prevention + fragmented QRS complex on 12-lead ECG
4. Accessibility of renal vasculature (determined by renal angiography)
5. Ability to understand the requirements of the study
6. Willingness to adhere to study restrictions and comply with all post-procedural follow-up requirements

6.2 EXCLUSION CRITERIA

1. Patient taking a Class I or III antiarrhythmic drug, unless required for an atrial arrhythmia

2. Planned to undergo a cardiac VT ablation procedure
3. NYHA Class IV Congestive Heart Failure
4. MI within 30 days
5. Known renovascular abnormalities that would preclude RSDN (e.g., renal artery stenosis, previous renal artery stenting or angioplasty)
6. Baseline orthostatic hypotension
7. End stage renal failure on hemodialysis
8. Life expectancy <1 year for any medical condition
9. Known pregnancy or positive β -HCG within 7 days of procedure.
10. Coronary Artery Bypass Graft (CABG) within 30 days of the procedure.

7. STUDY PHASES:

This study is divided into two phases: the initial phase (to include 50 patients) followed by the remaining 412 patients, for a total of 462 patients. The initial 50 subjects will be conducted at up to 10 sites (please see Section 1.1 for a listing of sites). An interim safety analysis for the primary endpoint will be conducted when the initial 50 subjects have completed the 6-month follow up visit.

7.1 CLINICAL CENTERS

The study will be conducted in up to 20 sites (with a maximum of 10 sites during the initial phase) in the United States and Europe. Each clinical center will be required to obtain IRB approval for the protocol and consent (and their revisions) in a timely fashion, to recruit patients, to collect data and enter it accurately in the electronic data capture (EDC) system, to faithfully follow the protocol and adhere to the standards of Good Clinical Practice (GCP). In addition, centers will be required to provide the DCC with the information necessary for interim, annual, and final reports, to provide source documents, data and regulatory documents for study monitors, provide prompt responses to DCC inquiries, and to participate in analyses and reporting of study results.

7.1.1 INVESTIGATOR PROFILE

All cardiologists, coordinators and other investigators in the study must complete the Investigator Profile form, including hospital affiliation, address, telephone, fax, beeper and email information. The cardiologist and coordinator must email or fax their CV, Conflict of Interest Statement and Financial Disclosure Certification, and Institutional Health Insurance Portability and Accountability Act (HIPAA) Certificates to the DCC.

7.1.2 QUALIFICATIONS AND TRAINING

Clinical investigators will be electrophysiologists with expertise in atrial fibrillation ablation. The certified operator will either perform the ablation and renal denervation on their own patient, or participate in the ablation and renal denervation of an enrolled patient. Sites will be limited to two operators per site. The clinical site Principal Investigator will be responsible for overseeing the ongoing performance of the other participating investigator at that site over the course of the study.

All clinical site investigators and coordinators will be trained by the DCC in the specifics of the protocol at a site initiation visit in advance of patient enrollment. Each site will have technical support provided by Boston Scientific for each of its first five patients. In addition, the investigators and coordinators will undergo a separate training session to gain familiarity with the electronic data capture system.

7.1.3 CONFLICT OF INTEREST AND FINANCIAL DISCLOSURE AGREEMENT

This statement verifies that all investigators have no conflict of interest with any institution that may influence their participation in this study. All investigators need to complete this statement. Investigators will also submit a financial disclosure agreement.

7.1.4 SITE APPROVAL

The following documents must be collected prior to site approval:

- Clinical Study Agreement
- Clinical site IRB roster
- Clinical site IRB approval, version and date for protocol and consent
- Clinical Center Laboratory Certification

A signed agreement between the clinical site and the DCC (Icahn School of Medicine at Mount Sinai) is required prior to site initiation. Prior to enrolling a patient, representatives from the DCC will conduct a site initiation for all investigators, coordinators, and any other health care professionals who may be involved in the study (e.g. engineers, social workers).

8. PATIENT ENROLLMENT AND WITHDRAWAL:

This will be a multicenter trial. Patients meeting the study inclusion criteria will be identified in the outpatient or inpatient setting by one of the study sites' primary or co-investigators. In essence, patients will be followed by one of the study site primary or co-investigators. Sites will be limited to enrollment of no more than 90 patients at their clinical site.

The study will typically be described (including the risks and benefits) during the initial clinic or hospital visit. Consent will typically be obtained at the time of the initial assessment if it is clear that the patient truly understands the nature of the study. Alternatively, the patient will be allowed to take a copy of the consent form home to contemplate whether they would like to be enrolled in the study. A sample consent form can be found in Appendix 1. Only patients who voluntarily provide consent will be included in this study. Patients will be considered enrolled once they have signed informed consent. Consent will be obtained prior to undergoing the ablation procedure. Patients will be able to withdraw from the study at any point without compromising their medical care.

Consent must be obtained either before, or within 24 hours of ICD placement. The patient may undergo ICD placement up to 1 month (30 days) before randomization. The patient must undergo either ICD placement and Renal Angiography (Control Group) or ICD placement and RSDN (Study/Experimental Group) within 1 month (30 days).

[figure not shown]
8.1 ROLL-IN PHASE

Each site has the option of enrolling one patient as part of a roll-in phase. Each roll-in patient will have renal angiography and renal sympathetic denervation performed. Patient data on these roll-in patients will not be used for the final analysis.

- Roll-in patients will be required to sign the study ICF, but will not be randomized.

- Although the data will not be used for the primary analysis, patients will be asked to adhere to the same follow up schedule of visits as randomized patients.
- As per FDA, roll-in patients will count toward the enrollment ceiling.
- The CRF must be adjusted to clearly reflect roll-in patients from randomized patients.

9. Pre-Procedure and Ablation Study Design Flow-Chart

9.1 PRE- AND ABLATION PROCEDURE

9.1.1 PRE-PROCEDURE

The following tests and procedures will occur before the ablation (within 30 days prior to randomization unless stated below):

- Recording of patient medical history (including details of VT both clinical/ICD)
- Recording medication history (including all AAD ever used, duration of use)
- Obtain β -HCG in females of child bearing age the morning of the procedure as per usual clinical practice
- Baseline assessment of arrhythmia burden and type: Office/inpatient records, ICD interrogation report
- If performed for any reason, collect any pre-procedural imaging: MRI/CT and Renal Ultrasounds within 6 months of procedure
- Baseline laboratory, including complete blood count, standard electrolyte panel, renal function, and brain natriuretic peptide levels.
- Baseline Transthoracic Echocardiogram within 3 months of procedure
- Baseline Office blood pressure. Proper blood pressure measurement technique is essential: i) patient should sit quietly in a chair with his/her back supported for 5 minutes before taking the measurement; ii) use of the correct cuff size with the air bladder encircling at least 80% of the arm (the adult large cuff for the majority of patients); iii) support the arm at heart level during the cuff measurement; iv) a minimum of 2 readings should be taken at intervals of at least 1 minute and the average of those readings should be taken to represent the patient's blood pressure; v) the blood pressure should be measured
- Consent must be obtained either before, or within 24 hours of ICD placement. The patient may undergo ICD placement up to 1 month (30 days) before randomization. The patient must undergo ICD placement and Renal Angiography (Control Group) or ICD placement and RSDN (Study/Experimental Group) within 1 month (30 days). All ICDs must be devices from Boston Scientific (either single-, dual-, subcutaneous, or biventricular devices).
- Randomization into one of two groups will be performed by opening the Randomization envelope after Renal Angiography.

Study/Experimental Group: These subjects will undergo catheter-based sympathetic renal denervation.

[figure not shown]
Placebo Control Group: These subjects will receive no further intervention.

9.1.2 PRE-PROCEDURE MEDICATION MANAGEMENT

Patients should not be taking any Class I or III anti-arrhythmic agents during this study unless required for atrial arrhythmia. After the ablation procedure, patients should receive either an antiplatelet agent (aspirin, clopidogrel, etc.) or anticoagulant (warfarin, dabigatran, etc.) for at least 1 week. Further decisions regarding the peri-procedural management of other cardiovascular (including anti-coagulant and anti-thrombotic agents) and non-cardiovascular medications should be as per clinical practice – but every effort should be made to maximize beta-blocker therapy, ACEI/ARB, and spironolactone therapy as per the guidelines.

9.1.3 RENAL SYMPATHETIC ABLATION PROCEDURAL DETAILS

- Patients will be brought to the electrophysiology laboratory in a fasting state
- Patient sedation or anesthesia will be administered according to standard EP lab protocol.
- Vascular access will be achieved in standard fashion.
- IV heparinization will be instituted. Full systemic anticoagulation will be instituted as per standard hospital procedures to a target ACT of 250 seconds or greater (or equivalent level depending on testing system performed).
- Abdominal aortography will be performed to assess the renal arteries for the suitability of catheter-based renal denervation in all patients. For those patients in whom the angiogram demonstrates that the renal anatomy is inappropriate for the RSDN procedure (small renal arteries, extensive atherosclerosis, renal stenosis, etc.), the patient will be excluded from the study as a screen failure. The patient's baseline information will be collected but no further follow-up required (beyond assessing for any adverse events related to the procedure). If the renal arteries are deemed suitable for RSDN, the patient will then undergo randomization.
- Randomization will be done by permuted-block randomization centrally and will be stratified by site. Allocation concealment shall be maintained at all sites by the use of a web-based central randomization scheme. The operating physician controlling the delivery of ablative energy will be aware of the outcome. This approach has been selected to minimize (1) study bias and (2) placebo effect. The randomization schema will be blocked by size for each site.
- Catheter-based sympathetic renal denervation will be performed using the Vessix balloon ablation catheter for denervation (see image below). The operating physician will manipulate the ablation catheter into the renal arteries as per standard operating procedures.

- The Vessix catheter is available in various sizes, and can be used to treat arteries between 3 mm and 7 mm in diameter and more than 20 mm in length. Radiofrequency energy is delivered via 8 electrodes to four distinct sites within the artery in a bipolar fashion. As with other renal denervation procedures, this catheter delivers four lesions in the artery which are separated along the length of the artery and are also separated orthogonally in different planes (anterior, inferior, posterior, and superior).
- The Vessix generator is pre-programmed with a temperature-controlled treatment algorithm. Energy is delivered to achieve a temperature of 68°C. Treatment time is 30 seconds. Average power is approximately 1 watt per electrode and is displayed on the generator screen during treatment. The system is designed to automatically deliver the proper amount of energy to achieve the appropriate temperature. The user does not need to (nor can he/she) adjust or set any of the biophysical parameters when using this system. The generator uses a proprietary algorithm (including impedance measurement) to determine appropriate apposition with the vessel wall. Electrodes which do not have appropriate apposition (such as those extending into the aorta) are automatically disabled by the generator.
- Only one catheter placement is required in most renal arteries. If the operator determines that the initial placement is unsatisfactory to treat the full length of the artery, a second activation will be permitted in a different location. No more than two catheter activations will be allowed in each renal artery.
- After delivery of a complete lesion (30 seconds), no further testing is required to ensure renal denervation. Physiologic endpoints for renal denervation have not been standardized.

9.2 POST-PROCEDURE

9.2.1 POST-PROCEDURE FOLLOW UP

- All patients will be monitored to verify vascular hemostasis prior to discharge from the hospital.
- All patients will receive either oral aspirin (81-325 mg QD) or clopidogrel (75 mg QD) or warfarin or one of the NOACs (dabigatran, rivaroxaban, Apixaban) for at least 1 week upon discharge.
- Medication and adverse event review will be performed prior to discharge.
- Complications including vascular, stroke, heart failure etc., and presence of ventricular arrhythmias will be documented.
- ICD programming: (see below section 9.2.3)
- The total number of episodes of VT, ATP, and Shocks will be documented at all visits.
- The follow-up includes:
 - 1 Month (\pm 14 days):
 - History and Physical
 - ICD interrogation
 - Office BP measurements (x2) including orthostatics
 - Review of Medications and Adverse events
 - 6 Months (\pm 30 days):
 - History and Physical
 - ICD interrogation
 - Office BP measurements (x2) including orthostatics
 - Lab tests (CBC, Electrolytes, BUN/Cr)
 - BNP Level

- Review of Medications and Adverse Events
 - Repeat Renal Ultrasound or MR/CT Angiography
- 12 Months (\pm 30 days):
 - History and Physical
 - ICD interrogation
 - EKG
 - Office BP measurements (x2) including orthostatics
 - Lab tests (CBC, Electrolytes, BUN/Cr)
 - Blood for Renal Hormones (OPTIONAL)
 - BNP Level
 - Review of Medications and Adverse Events
 - Repeat TTE
- 18 Months (\pm 30 days):
 - History and Physical
 - ICD interrogation
 - Office BP measurements (x2) including orthostatics
 - Review of Medications and Adverse Events
- 24 Months (\pm 30 days):
 - History and Physical
 - ICD interrogation
 - Office BP measurements (x2) including orthostatics
 - Lab tests (CBC, Electrolytes, BUN/Cr)
 - BNP Level
 - Review of Medications and Adverse Events
- 36 Months (\pm 30 days):
 - History and Physical
 - ICD interrogation
 - Office BP measurements (x2) including orthostatics
 - Lab tests (CBC, Electrolytes, BUN/Cr)
 - BNP Level
 - Review of Medications and Adverse Events

Patients will be followed for a maximum of 36 months until the final patient reaches the 18 month follow-up time point. Once the final patient reaches the 18 month follow-up time point, all follow-ups will cease.

9.2.2 POST-PROCEDURE MEDICATION MANAGEMENT

- Standard cardiovascular medications are left up to the discretion of the investigator – but BBLs, ACEI, ARBs and aldosterone antagonist use is recommended as per standard guidelines.
- Class I and III antiarrhythmic drug use is not permitted in this study, unless required for atrial arrhythmias.
- Therapeutic anticoagulation (example Warfarin or equivalent agent) beyond the requisite 1 week post-procedure time point is at the discretion of the patient's physician.

9.2.3 ICD PROGRAMMING

The following programmed detection and therapy parameters should be used to optimize therapy delivered to the subject during the course of the study for both the Catheter Ablation Group (Treatment) and Control Group:

ICD Programming Requirements

Arrhythmia	Programming Strategy
VT Zone	175-195 bpm
VF Zone	200 bpm. ATP to 250 bpm
Monitor Zone	130-170 bpm
VT Therapy	ATP – recommended. Programmed at investigators discretion
SVT Discriminators	Should be “ON” in VT zone. Programmed at investigators discretion.

Device Specific Detection Parameters

Arrhythmia	Boston-Scientific
VF	5s (1-25s std, but would be approx.3-10 beats)
VT	5s
Monitor	
Comments	

9.3 SAFETY

We anticipate no significant increase in adverse events as compared to the standard ICD implantation or renal angiography procedure. The local site primary investigator will oversee the safety of the study at his/her site. All adverse events will be reported to the Data Coordinating Center (Icahn School of Medicine at Mount Sinai). Adverse events will be monitored and tallied for each 50 patients enrolled in the study and presented to the Data Safety Monitoring Board. The PI will also be present at the meetings to relate any pertinent trial information. However, recommendations are solely up to the discretion of the DSMB.

9.3.1 INTERIM ANALYSES

An interim safety analysis will be performed after enrollment of the first 50 subjects (25 controls, 25 study group). This analysis will be presented to the DSMB, which has the authority to terminate the study prematurely if an increase in adverse events is encountered. The trial will be terminated early if severe procedure-related adverse events occur in more than 15% of patients in the treatment arm. If the DSMB determines the trial should be stopped early either because of safety concerns, or otherwise modified, the DSMB will prepare formal written recommendations to the PI to consider final action. Moreover, any pressing safety concerns that the DSMB identifies will be verbally communicated to the PI as soon as possible, prior to written documentation.

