Design:	This study is a prospective, multicenter, single-blinded, randomized (1:1) control trial evaluating the effectiveness of RSDN in the primary prevention of ICD therapy in patients with ischemic or non-ischemic ventricular dysfunction who are to receive an ICD for either i) secondary prevention, or ii) primary prevention + inducible VT by programmed ventricular stimulation at the time of ICD implantation. These patients will be randomized to ICD alone or ICD + RSDN. Subjects will only be eligible for this study if they are \geq 18 years of age and have a history of structural heart disease (post-MI, dilated cardiomyopathy, sarcoid myopathy, hypertrophic cardiomyopathy, etc.), and are planned for ICD implantation for: i. Secondary prevention (e.g.: VT/VF arrest, sustained VT, syncope/inducible VT) ii. Primary prevention + inducible MMVT during induction via ICD lead testing. In addition, eligible patients will have accessible renal vasculature (as determined by renal angiography).
	The patient will be blinded to the results of randomization. Once randomized, study group subjects will undergo a strategy of catheter-based renal sympathetic denervation + ICD implantation (if not already present). Control patients will receive standard ICD implantation alone (if not already present). Follow-up will be conducted in regular intervals over a 12-month period.
Enrollment:	Total: 462 subjects (231 control group, 231 study group)
	An interim safety analysis will be performed after the first 50 subjects (25 control group, 25 study group) have completed their 6-month follow-up visit.
Clinical Sites:	
• Icahn School of Medicine at Mount Sinai• Homolka Hospital, Prague, Czech Republic• Heart Center U SV. Anny Hospital, Brno, Czech Republic• Massachusetts General Hospital• Regional Cardiology, Sacramento, California• Medical University of South Carolina• Florida Hospital, Orlando, Florida

	
 • Other Sites TBD
Time Course:	Enrollment: Over 4 years

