In an initial pilot study, an irrigated radiofrequency catheter (Celsius Thermocool F-Curve RF catheter, Biosense-Webster, Inc., Diamond Bar, California) was used in 20 patients with ischemic or non-ischemic ventricular dysfunction, who were scheduled to receive an ICD for either i) secondary prevention, or ii) primary prevention + inducible VT by programmed ventricular stimulation at the time of ICD implantation ([name], unpublished observation). Although we have favorable single-operator, single-center safety data in another RSDN trial, preliminary review of the six-month renal ultrasound data provided a higher than expected event rate of renal artery stenosis. As such, the protocol has been amended to allow for the use of a dedicated renal sympathetic denervation catheter system: the Vessix™ Renal Denervation System (Boston Scientific, Quincy, Massachusetts).

4. SCHEDULE OF TREATMENT AND TESTS:

TABLE 1:

	Baseline	Procedure*	Discharge	1, 6,12,18,24,36 months**
Type of visit	Office	Hospital		Office
Informed Consent	X			
Brief History & Physical	X			X
Blood Laboratory Testing: CBC, Electrolytes, BUN/ Creatinine, BNP	X			X (6, 12, 24, 36m)
Blood for Renal Hormones (OPTIONAL*)	X			X (12m)
TTE	X			X (12 m)
Renal Angiography		X		
Ultrasound or MR/ CT Angiography				X (6 m)
Randomization		X		
Renal Sympathetic Denervation		X		
ICD Interrogation	X			X
EKG	X			X (12m)
Office BP Measurements (including orthostatic BPs)	X			X
Medications	X		X	X
Adverse Events		X	X	X

* Hormonal measurements are optional in cases where the cost would be prohibitively burdensome to patients or hospital/clinic facilities are not available to allow for their measurement.

** - Visit windows – 1 Month (\pm 14 days); 6, 12, 18, 24, 36 Months (\pm 30 days)

5. ENDPOINTS:

5.1 PRIMARY ENDPOINT:

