10.7 INTERIM MONITORING GUIDELINES

The objectives of interim monitoring are to (1) monitor for safety, (2) track participant accrual rates, and (3) monitor the primary and secondary outcomes for early evidence of efficacy, harm or futility. To accomplish this, summaries of data quality, accrual, adherence, distribution of baseline factors, toxicity, study endpoints and other analyses as requested will be prepared for review by the Data Safety Monitoring Committee (DSMB).

The primary outcome of the trial, rate of first event requiring any ICD therapy, is the basis for formal interim analysis plan that follows. One interim analysis and one final analysis are planned for this trial, for a total of 2 analyses. These analyses will be performed when 0.5 and 1.0 fraction of the total number of events will have been observed. Since this study will have a target number of events of 70, we will have approximately 35 events observed between each analysis time.

We will use an alpha-spending O'Brien-Fleming sequential procedure as a guideline for decision making. At the interim analysis the value of the test statistic will be compared with the alpha spending function critical values. The two alpha values will be set at 0.0054 at the interim analysis and 0.0492 at the final analysis, which equate to critical values of 2.782 and 1.967 respectively. This monitoring plan maintains the overall type I error at 0.05, given one interim analysis.

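### The first-50 safety look has two conflicting triggers, and the one beside the 15% stopping rule can fall before most treated patients have had 6-month renal imaging

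*Combined protocol and SAP*

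**What the plan says.** Three places describe one safety look at the first 50 subjects.

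- Section 9.3.1: "An interim safety analysis will be performed after enrollment of the first 50 subjects (25 controls, 25 study group". The same paragraph holds the decision rule: "The trial will be terminated early if severe procedure-related adverse events occur in more than 15% of patients in the treatment arm".
- Protocol Summary, Enrollment row: "An interim safety analysis will be performed after the first 50 subjects (25 control group, 25 study group) have completed their 6-month follow-up visit".
- Section 7, Study Phases: "An interim safety analysis for the primary endpoint will be conducted when the initial 50 subjects have completed the 6-month follow up visit".

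Section 8 defines enrollment: "Patients will be considered enrolled once they have signed informed consent". Consent comes before renal angiography, and randomization follows angiography (9.1.1, 9.1.3).

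The schedule in Section 4 and the visit list in 9.2.1 put post-procedure renal ultrasound or MR/CT angiography at the 6-month visit only. Section 3.1 explains why the catheter was changed: "preliminary review of the six-month renal ultrasound data provided a higher than expected event rate of renal artery stenosis". Section 5.2 lists renal artery stenosis among procedure-related adverse events, without a severity grade.

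On efficacy monitoring, Section 10.7 says: "One interim analysis and one final analysis are planned for this trial, for a total of 2 analyses". The interim is set at half of the 70 target events.

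**The concern.** Whoever convenes the DSMB cannot follow all three passages. The stopping rule sits beside the earlier trigger, so a literal reading of 9.3.1 applies a stated termination threshold before the one scheduled test that can show renal artery stenosis has been done in most of the treated patients. A result below 15% at that point would say something about acute procedural harm and little about stenosis, yet it could be taken as clearing the first phase.

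Section 7 adds a second uncertainty. It calls the look a safety analysis but ties it to the primary endpoint, which is ICD therapy or incessant VT. The reader cannot tell what is to be analysed.

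**Working it through.** The plan gives no figure to reproduce here. The contradiction is textual, and the arithmetic only sizes it.

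**1. The triggers side by side.** Section 9.3.1 acts on enrollment. The Protocol Summary and Section 7 act "when the initial 50 subjects have completed the 6-month follow up visit" or in equivalent terms. Two passages agree and one differs, and the one that differs holds the rule. Read with Section 8, the 9.3.1 trigger could be met before the latest patients have had their procedure. The 25/25 split in 9.3.1 suggests that randomized subjects were meant, but the text does not say so.

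**2. Imaging available at the enrollment trigger.** Inputs from 10.6: 462 patients, 48 months, non-uniform accrual of unstated shape. Average rate: 462/48 = 9.625 per month. I assume cumulative accrual N(t) = 462 × (t/48)^k, where k = 1 is uniform and k = 1.5 to 3 are assumed ramp-ups.

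- Month of the 50th subject: T = 48 × (50/462)^(1/k)
- Share of the 50 past 6 months: ((T − 6)/T)^k, or 0 if T is under 6
- Treated patients past 6 months: 25 × share
- Further subjects enrolled in the next 6 months: 462 × ((T + 6)/48)^k − 50

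| k | T (months) | Share past 6 months | Treated, of 25 | Further subjects |
|---|---|---|---|---|
| 1 | 5.2 | 0 | 0 | 58 |
| 1.5 | 10.9 | 0.30 | 7.5 | 47 |
| 2 | 15.8 | 0.38 | 9.6 | 45 |
| 3 | 22.9 | 0.40 | 10.0 | 51 |

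If every scan were done at the early edge of the 30-day window (month 5), the treated counts become 0.9, 10.0, 11.7 and 11.9, still under half. Counting the trigger from consent would lower them, because the procedure comes later. Slower accrual would raise them: if the first 50 arrived at a constant rate over 12 months, (12 − 6)/12 × 25 = 12.5 would be past 6 months, and over 24 months, 18.8. Under the 6-month-visit trigger, imaging is due in all 25.

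**3. What the rule needs.** 15% of 25 is 3.75, so at least 4 events (4/25 = 16%; 3/25 = 12%). As an illustration only, assume a 5% acute severe rate plus a further rate seen only on 6-month imaging and counted as severe. The probability of at least 4 events in 25 is then:

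| Imaging-only rate (assumed) | None imaged | 10 imaged | All 25 imaged |
|---|---|---|---|
| 10% | 0.03 | 0.18 | 0.53 |
| 15% | 0.03 | 0.29 | 0.77 |
| 20% | 0.03 | 0.41 | 0.90 |

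These rates are not in the documents. If imaging-only stenosis does not count as severe, every cell is 0.03 and the trigger makes no difference by this route.

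**4. Information on the primary endpoint.** Constant hazards from the 18-month rates in 10.6 are −ln(0.81)/18 = 0.01171 and −ln(0.886)/18 = 0.00672 per month. At exactly 6 months each: 25 × (1 − e^(−6 × 0.01171)) + 25 × (1 − e^(−6 × 0.00672)) = 1.7 + 1.0 = 2.7 events. At uniform accrual the later look falls at month 5.2 + 6 = 11.2, with mean follow-up 6 + 5.2/2 = 8.6 months. Putting 8.6 for 6 gives 2.4 + 1.4 = 3.8 events. The formal interim in 10.7 needs about 35.

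**The case against.** The strongest reply is that other oversight covers the gap. Section 9.3 has adverse events tallied for the DSMB at every 50 enrolled, 9.3.3 has the DSMB review data every 6 months or as needed, and 9.4.7 sets serious adverse event reporting. Section 9.3.1 does not expressly confine the 15% rule to one look. This stands: stenosis data would reach the DSMB later. It does not settle when the formal look takes place. The tally is itself triggered by enrollment, and neither 9.3 nor 9.3.3 restates the 15% rule.

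An early look also has a purpose, since dissection and bleeding show early. That stands too, and is why the tally should stay.

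Three stronger readings are tempting, and the documents do not support them.

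- A reader might infer that stenosis is a known harm of the device under test. Section 3.1 reports the signal before the protocol was amended to allow the Vessix system, and no signal with Vessix is reported. Stenosis is a risk worth watching, no more.
- A reader might infer that nobody would have been imaged. That holds only near uniform accrual; 10.6 states non-uniform accrual, and 7.1 limits the initial phase to 10 of up to 20 sites.
- A reader might infer that Section 7 adds an efficacy look outside the alpha plan. It names no between-arm test, boundary or efficacy decision, and the Protocol Summary calls the look a safety analysis only. The phrase is ambiguous; it does not show that alpha is spent.

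**Conclusion.** The contradiction is certain and rests on no assumption: 9.3.1 conflicts with the Protocol Summary and Section 7 on when the first-50 look occurs.

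Its size depends on accrual. Under the 9.3.1 trigger, 0 to 1 of 25 treated patients would have 6-month imaging at the average rate, and roughly 7 to 10 under the assumed ramp-ups, so most would lack it. That would cease to hold if the first 50 took longer than about 12 months at a constant rate. The effect on the chance of crossing 15% cannot be fixed from the documents, because neither the event rates nor the meaning of severe is given.

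The gap concerns one formal look with a stated decision rule, not safety oversight as a whole. The Section 7 wording on the primary endpoint is a smaller ambiguity to clear up at the same time. With 3 to 4 events expected, an efficacy comparison there would be uninformative anyway.

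**What to change.** - Reconcile the three passages to one trigger for the formal look. Align 9.3.1 with the two that already agree: the first 50 randomized subjects have completed the 6-month visit, with renal imaging available.
- Keep the tally per 50 enrolled in 9.3 as the early review of acute harms.
- In Section 7, replace the reference to the primary endpoint with a statement that the look is safety-only, makes no between-arm efficacy comparison and spends no alpha, consistent with 10.7.
- Have the sponsor state in 9.3.1 whether stenosis found only on imaging counts toward the existing rule. The threshold itself is not at issue here.

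The change is to wording in two sections. Its cost is delay: the formal look comes about 6 months later. At average accrual 6 × 9.625 ≈ 58 more subjects, about 29 of them assigned RSDN, would enroll by then if enrollment is not paused (about 45 to 51 in total under the assumed ramp-ups). The tally and the 6-monthly DSMB reviews continue meanwhile, which keeps that cost small.
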